7.3.2.2. Actual and Change from Baseline in Week Y Total Daily Steps

Summary descriptive statistics of the actual Week Y TDS and change from baseline in TDS for each study week (1 through 12) will be presented overall, and by CE-COPD status and by CE-COPD severity (Yes: severe, moderate; No) using the ankle accelerometry analysis set.

7.4. Accelerometry: Sleep Disruption Index

7.4.1. Sleep Disruption Index Definition

The SDI for analysis in this study will consist of the following measures, which correlate significantly with SABA rescue use (Krouse et al. 2008) and the composite score derived from the summation of these 3 measures.

- (i) Nighttime Average Sleep Latency Time ($r=0.78$)
- (ii) Longest Nighttime Wake Episode ($r=0.73$)
- (iii) Total Time Awake at Night ($r=0.65$)

Study Day X and Week Y SDIs are defined as follows:

Study Day X Nighttime Average Sleep Latency Time: The nighttime average sleep latency time for study day X is the nighttime average sleep latency time recorded by wrist accelerometry on study day X . If nighttime average sleep latency time is missing on Study Day X , then the average nighttime average sleep latency time of the 7 days preceding study day X is computed and assigned to Study Day X .

Week Y Nighttime Average Sleep Latency Time: The nighttime average sleep latency time for Week Y is computed using the set of nighttime average sleep latency times recorded by wrist accelerometry during a given week on study. The average will be calculated as the sum of the daily nighttime average sleep latency times divided by the number of days with nonmissing nighttime average sleep latency times.

Study Day X Longest Nighttime Wake Episode: The longest nighttime wake episode for study day X is the longest nighttime wake episode calculated as described in Section 4.2.5 on study day X . If longest nighttime wake episode is missing on Study Day X , then the greatest longest nighttime wake episode of the 7 days preceding study day X is computed and assigned to Study Day X .

Week Y Longest Nighttime Wake Episode: The longest nighttime wake episode for Week Y is the greatest longest nighttime wake episode calculated as described in Section 4.2.5 during a given week on study.

Study Day X Total Time Awake at Night: The total time awake at night for study day X is the total time awake at night time recorded by wrist accelerometry on study day X . If total time awake at night is missing on Study Day X , then the average total time awake at night of the 7 days preceding study day X is computed and assigned to Study Day X .

Week Y Total Time Awake at Night: The total time awake at night for Week Y is computed using the set of total time awake at night times recorded by wrist accelerometry during a given week on study. The average will be calculated as the sum of the total time awake at night times divided by the number of days with nonmissing total time awake at night times.

Study Day X SDI Composite Score: The SDI composite score for study day X is sum of nighttime average sleep latency time, longest nighttime wake episode and total time awake at night on study day X .

Week Y SDI Composite Score: The SDI composite score for Week Y is the sum of nighttime average sleep latency time, longest nighttime wake episode and total time awake at night for Week Y .

The SDIs are computed for those patients in the wrist accelerometry analysis set.

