9.5. Endpoint Analysis

9.5.1. Endpoints

The endpoints of the trial are the primary outcome measure (ie, CE-COPD) and the primary outcome predictor (ie, albuterol use) alone or in combination with secondary predictors (ie, other study data, including inspiratory flow, SDI, TDS, disease state at baseline, and demographics at baseline) of CE-COPD. These predictors of CE-COPD will be modeled to determine which patterns best predict the subsequent development of CE-COPD. For albuterol use, examples of correlates of CE-COPD of interest include (1) the total number of inhalations in the days preceding the peak of a CE-COPD, (2) the number of days prior to the peak of a CE-COPD when albuterol use increased, and (3) the number of albuterol uses in the 24 hours preceding a CE-COPD.

Albuterol use and inspiratory flow values are obtained from the eMDPI, SDI is obtained for a subset of patients (n=100) from an accelerometer worn on the wrist, and TDS is obtained for a subset of patients (n=100) from an accelerometer worn on the ankle. Baseline disease state and demographic information will be obtained at screening.

The following 8 surrogate measures of sleep disruption are available from the accelerometer worn on the wrist: (i) sleeptime average total time in bed, (ii) sleeptime average total sleep time, (iii) sleeptime average sleep latency time, (iv) sleeptime average wakening after sleep onset, (v) total time awake at night, (vi) longest sleeptime wake episode, (vii) daytime average minutes asleep, and (viii) longest daytime sleep episode.

The SDI for analysis in this study is the composite endpoint derived from the summation of sleeptime average sleep latency time, longest sleeptime wake episode, and total time awake at night. These 3 surrogate measures were correlated significantly with SABA rescue use (sleeptime average sleep latency time ($r=0.78$), longest sleeptime wake episode ($r=0.73$), and total time awake at night ($r=0.65$) ([Krouse et al 2008](#)).

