4.2.3. Inhalational Flow Values

The baseline inspiratory flow values are computed using the set of inhalations taken by the patient during study day 1 through day 7. Among these inhalations, the inhalation with the highest MIF value is considered the ‘baseline inhalation’. The baseline MIF, inhalational volume, inhalation duration, and time to MIF values are those of the identified ‘baseline inhalation’. If no inhalations were taken during study day 1 through study day 7, the ‘baseline inhalation’ is the first available inhalation after study day 7.

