4.2.5. Sleep Parameters

There are 8 measures of sleep disruption: (i) nighttime average total time in bed, (ii) nighttime average total sleep time, (iii) nighttime average sleep latency time, (iv) nighttime average wakening after sleep onset, (v) total time awake at night, (vi) daytime average minutes asleep, (vii) longest daytime sleep episode and (viii) longest nighttime wake episode. The first 7 sleep parameters are provided via Philips accelerometry and longest nighttime wake episode is derived from the accelerometry data as follows:

The sleep interval data provided via Philips accelerometry includes the activity state ("sleep"/"awake") every 30 seconds during the sleep interval. The number of successive 30 second "awake" states occurring between "sleep" states within the sleep interval is summed to determine the duration of a given "awake" state. The longest nighttime wake episode is the summated "awake" state with the longest duration during the sleep interval.

The baseline value of a given sleep parameter (eg, nighttime average total time in bed) is the average sleep parameter (eg, nighttime average total time in bed), computed using the sleep parameter (eg, nighttime average total time in bed) values captured by accelerometry during study day 1 through day 7. The average will be calculated as the sum of the average sleep parameter divided by the number of days with nonmissing values of the average sleep parameter. If no sleep parameter data are available for study day 1 through study day 7, the 'baseline value of a given sleep parameter' is the first available valid sleep parameter value after study day 7.

Baseline sleep parameters are computed for those patients in the wrist accelerometry analysis set.

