5.3. Demographics and Baseline Characteristics

Patient demographic and baseline characteristics will be summarized for all patients in the ITT analysis set using descriptive statistics. Demographic and baseline characteristics will include: age, sex, race, ethnicity, weight, height, and body mass index (BMI), vital signs, TDS, inhalational flow values and SDIs.

The formula for BMI is: $BMI = \frac{\text{weight}}{\text{height}^2}$,

where weight is in kilograms (kg), height in meters (m) and BMI is kg/m².

Baseline inhalational flow values include MIF, inhalational volume, inhalation duration, and time to MIF. Baseline SDIs include nighttime average total time in bed, nighttime average total sleep time, nighttime average sleep latency time, nighttime average wakening after sleep onset, total time awake at night, daytime average minutes asleep, longest daytime sleep episode and longest nighttime wake episode.

Demographics and baseline characteristics will be summarized by analysis set (ITT analysis set and the ankle and wrist accelerometry analysis sets).

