7.4.2. Analysis Methods for Sleep Disruption Indices

7.4.2.1. Actual and Change from Baseline in Study Day X Sleep Disruption Indices Prior to the Peak of a CE-COPD

Among patients in the wrist accelerometry cohort who experienced a CE-COPD, summary descriptive statistics of nighttime average sleep latency time, longest nighttime wake episode, and total time awake at night and change from baseline in these 3 measures of SDI at 1 day (eg, the 24-hour period on the day prior to the date of the CE-COPD symptom peak) and at 3, 5, 7, 10, 14 and 21 days preceding the peak of a CE-COPD, will be presented for all CE-COPDs and by moderate CE-COPDs and severe CE-COPDs.

Summary descriptive statistics of nighttime average sleep latency time, longest nighttime wake episode, and total time awake at night and change from baseline in these 3 measures of SDI will be presented for overall, by CE-COPD status, by CE-COPD severity (Yes: severe, moderate; No) and for the first occurrence of a single day increase of 20% from baseline use. For patients who experienced a CE-COPD, the single day increase of 20% from baseline use is defined as the increase prior to the exacerbation.

In addition, summary descriptive statistics of the maximum daily change from baseline nighttime average sleep latency time, longest nighttime wake episode, and total time awake at night, will be presented overall and by CE-COPD status and by CE-COPD severity. For patients who experienced a CE-COPD, the maximum daily change from baseline is the change prior to the exacerbation.

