7.4.2.2. Actual and Change from Baseline in Week Y Sleep Disruption Indices

Summary descriptive statistics of the absolute Week Y nighttime average sleep latency time, longest nighttime wake episode, total time awake at night, and SDI composite score and change from baseline in these 4 SDIs for each study week (1 through 12), will be presented overall, and by CE-COPD status and by CE-COPD severity.

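### Weekly change in longest nighttime wake episode sets the week's greatest night against a 7-night mean, so it shows an increase when sleep has not changed

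*SAP*

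**What the plan says.** **Baseline.** SAP 4.2.5 lists eight sleep parameters, with longest nighttime wake episode as item (viii), and gives one baseline rule for all of them, an average over study days 1 to 7: "The average will be calculated as the sum of the average sleep parameter divided by the number of days with nonmissing values". If those days hold no data, the first later value is used.

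**Weekly value.** SAP 7.4.1 switches to a maximum for this measure alone: "The longest nighttime wake episode for Week Y is the greatest longest nighttime wake episode calculated as described in Section 4.2.5". Weekly sleep latency and weekly total time awake are means of the nightly values.

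**Composite.** SAP 7.4.1 adds the three weekly components: "The SDI composite score for Week Y is the sum of nighttime average sleep latency time, longest nighttime wake episode" and total time awake. Protocol 9.5.1 gives the composite its standing: "The SDI for analysis in this study is the composite endpoint derived from the summation of sleeptime average sleep latency time", together with the other two components. SAP 4.2.5 defines no composite baseline, and the baseline list in SAP 5.3, which opens "Baseline SDIs include nighttime average total time in bed, nighttime average total sleep time, nighttime average sleep latency time", does not contain one.

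**Output.** SAP 7.4.2.2 tabulates absolute weekly values and change for the three measures and the composite: "SDI composite score and change from baseline in these 4 SDIs for each study week", overall and by CE-COPD status and severity. It is the only SAP section that summarizes the composite. The pre-peak tables in SAP 7.4.2.1 stop at the components: "longest nighttime wake episode, and total time awake at night and change from baseline in these 3 measures of SDI".

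**The concern.** A change from baseline should average zero when nothing has changed. Here it cannot, because the greatest of several nights lies above their mean whenever nights vary. A reader of the weekly change column would see longer wake episodes from Week 1 onward in patients whose sleep is stable.

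The neighbouring measures make this harder to spot. Latency, total time awake and total daily steps are means on both sides, so their Week 1 change is exactly 0, and a reader would expect the same here. The composite is the measure that the protocol names for analysis, and its weekly value contains the mismatched component.

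**Working it through.** The documents state no figure on this point, so there is nothing to reproduce. The check compares definitions and then works out the change expected with no true change.

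**Step 1. Week 1, no distribution needed.** SAP 4.5 sets Week 1 as study days 1 to 7, which are the baseline days. For valid nights x1 to xn,

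Week 1 change = max(x) − mean(x) ≥ 0,

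with equality only if all nights are equal. Assumed nights of 10, 12, 15, 20, 8, 25 and 14 min:

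- baseline = 104/7 = 14.9 min
- Week 1 value = 25 min
- Week 1 change = 25 − 14.9 = +10.1 min, from the same seven nights

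**Step 2. Later weeks.** Let E[n] be the expected maximum of n standard normal values: E[1] = 0, E[3] = 0.846, E[5] = 1.163, E[7] = 1.352. With independent normal nights and no true change, the expected weekly change is E[n] within-patient SD, where n is the number of valid nights in the week: +1.35 for 7, +1.16 for 5, +0.85 for 3.

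Other assumed shapes, 7 valid nights, simulated with 400,000 patients per run:

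| Nightly values | Offset (SD) | Unchanged patients showing an increase |
|---|---|---|
| Normal | +1.35 | 97% |
| Lognormal, CV 0.3 | +1.50 | 96% |
| Lognormal, CV 0.5 | +1.55 | 95% |
| Lognormal, CV 1.0 | +1.52 | 92% |
| Exponential | +1.60 | 93% |
| Normal, night-to-night autocorrelation 0.3 | +1.27 | 94% |
| Normal, night-to-night autocorrelation 0.6 | +1.08 | 88% |

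For the lognormal cases the offset is 45%, 77% and 152% of the mean night at CV 0.3, 0.5 and 1.0.

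**Step 3. Trend and group comparison.** The expected offset is the same in Week 1 and in later weeks if valid nights and variability do not change, so it shifts the whole series by a constant. It does not cancel if they differ. On the normal model, 7 against 3 valid nights a week gives 1.352 − 0.846 = 0.51 SD between two groups, or between two periods, with identical sleep.

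**Step 4. Composite.** Three baselines are natural. The sum of the component baselines and the mean nightly composite over days 1 to 7 both contain the mean wake episode, so the composite change carries the component's offset in full. The Week 1 composite contains the maximum, so it does not. The SAP does not choose.

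**Step 5. Daily inhalational flow, for comparison.** SAP 4.2.3 draws the baseline from the whole first week ("The baseline inspiratory flow values are computed using the set of inhalations taken by the patient during study day 1 through day 7") and takes the inhalation with the highest MIF. SAP 7.2.1 takes the highest of one day. With k independent normal inhalations a day and constant use, the expected daily MIF change is E[k] − E[7k]: −1.35, −1.14, −0.98 and −0.87 SD at k = 1, 2, 4 and 8. When use rises it becomes −0.67 (2 to 4 a day), −0.28 (2 to 8) and +0.07 (1 to 8).

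**The case against.** The strongest case against acting is that little depends on this column. It is descriptive, and it covers one component, and possibly the composite, in a subset planned at 100 patients. The t-test in SAP 7.1.2.3, the paired tests in 7.5.2.1 and the landmark plots in 7.5.2.2 do not use it. Absolute weekly values stand beside it. The daily sleep values in 7.4.2.1 set one night against a mean and are matched when that night was recorded. All of this stands, and it limits the consequences. It does not make the column right: the stated rule gives a non-zero expected change in stable patients.

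It can also be said that the week's greatest episode is a deliberate choice. As an absolute value it is unobjectionable; the fault lies only in subtracting a mean from it.

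Three stronger readings are tempting, and the documents do not support them:

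- *The composite's change is biased.* That depends on a baseline that the SAP leaves undefined. The gap is real; the bias is conditional on how it is filled.
- *The tables create a difference between patients with and without CE-COPD.* An offset common to both groups cancels. The documents give neither the variability nor the recorded nights by group.
- *The daily flow baseline is wrong in the same way and must be replaced.* A 7-day personal best is a defensible reference, and the offset changes size and even sign with use. Replacing it by the mean of the daily bests gives 0 at stable use but +0.47, +0.86 and +1.42 SD at 2 to 4, 2 to 8 and 1 to 8 a day, against −0.67, −0.28 and +0.07 now. It therefore enlarges the offset where use rises sharply, and the study expects use to rise before a CE-COPD.

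**Conclusion.** The definitions do not match, and the weekly change in longest nighttime wake episode is wrong in its level against zero. That it is never negative in Week 1 follows from the text alone. The upward offset in later weeks needs only some night-to-night variability. Its size, about +1.1 to +1.6 within-patient SD with 7 valid nights and less with fewer, rests on assumed distributions; the documents give no SDs, so the offset in minutes is unknown.

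The trend across weeks remains readable if recorded nights and variability are stable, and the CE-COPD comparison is distorted only if these differ between groups. No test or decision rule is touched. It should still be corrected before tables are produced, because the error is plain and the remedy small. Daily flow warrants a note and no change of baseline.

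**What to change.** 1. **Change column, SAP 7.4.1 and 7.4.2.2.** Derive the weekly change as the mean of the week's nightly longest wake episodes minus the mean over days 1 to 7. Keep the week's greatest as an absolute value only. Greatest of the week against greatest of days 1 to 7 is acceptable when the numbers of valid nights are equal. Otherwise it brings in its own offset: E[3] − E[7] = −0.51 SD for a 3-night week against 7 baseline nights, and +1.35 SD for a 7-night week where baseline falls back to a single later value (normal model).
2. **Composite.** State the baseline of the weekly SDI composite in SAP 4.2.5, and build it and the composite's change from the same matched components.
3. **Note on daily flow, SAP 7.2.2.1.** State that daily MIF change sets a one-day best against a 7-day best and varies with the number of inhalations that day, so it should be read with the actual values and that day's count.

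The cost is one derivation line, one definition, one note and some reprogramming, with no new data. A footnote is needed under option 1, because the displayed weekly greatest minus baseline will no longer equal the displayed change.

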7.4.2. Analysis Methods for Sleep Disruption Indices

7.4.2.1. Actual and Change from Baseline in Study Day X Sleep Disruption Indices Prior to the Peak of a CE-COPD

Among patients in the wrist accelerometry cohort who experienced a CE-COPD, summary descriptive statistics of nighttime average sleep latency time, longest nighttime wake episode, and total time awake at night and change from baseline in these 3 measures of SDI at 1 day (eg, the 24-hour period on the day prior to the date of the CE-COPD symptom peak) and at 3, 5, 7, 10, 14 and 21 days preceding the peak of a CE-COPD, will be presented for all CE-COPDs and by moderate CE-COPDs and severe CE-COPDs.

Summary descriptive statistics of nighttime average sleep latency time, longest nighttime wake episode, and total time awake at night and change from baseline in these 3 measures of SDI will be presented for overall, by CE-COPD status, by CE-COPD severity (Yes: severe, moderate; No) and for the first occurrence of a single day increase of 20% from baseline use. For patients who experienced a CE-COPD, the single day increase of 20% from baseline use is defined as the increase prior to the exacerbation.

In addition, summary descriptive statistics of the maximum daily change from baseline nighttime average sleep latency time, longest nighttime wake episode, and total time awake at night, will be presented overall and by CE-COPD status and by CE-COPD severity. For patients who experienced a CE-COPD, the maximum daily change from baseline is the change prior to the exacerbation.

7.4.2.2. Actual and Change from Baseline in Week Y Sleep Disruption Indices

Summary descriptive statistics of the absolute Week Y nighttime average sleep latency time, longest nighttime wake episode, total time awake at night, and SDI composite score and change from baseline in these 4 SDIs for each study week (1 through 12), will be presented overall, and by CE-COPD status and by CE-COPD severity.

7.5. Clinical Exacerbation of COPD

7.5.1. Definition of Clinical Exacerbation of COPD

A CE-COPD is the primary outcome measure of this study. In this study, a CE-COPD is an occurrence of either a “severe CE-COPD” or a “moderate CE-COPD.” “Mild CE-COPD” is defined below for investigator information but is not used either for entry criteria or as a measure in this study.

- Severe CE-COPD is defined as an event that involves worsening respiratory symptoms for at least 2 consecutive days requiring treatment with systemic corticosteroids (SCS; at least 10 mg prednisone equivalent above baseline [Table 2]) and/or systemic antibiotics and a hospitalization for CE-COPD.
- Moderate CE-COPD is defined as an event that involves worsening respiratory symptoms for at least 2 consecutive days requiring treatment with SCS (at least 10 mg prednisone equivalent above baseline [Table 2]), and/or systemic antibiotics, and an unscheduled encounter (such as a phone call, an office visit, an urgent care visit, or an emergency care visit) for a CE-COPD, but not a hospitalization.
- Mild CE-COPD is defined as a worsening of respiratory symptoms for at least 2 consecutive days requiring self-management by the patient, such as increased inhaler use, but not requiring treatment with SCS and/or antibiotics, nor an unscheduled visit of any kind.

Table 2: Systemic Glucocorticoid Treatment Equivalent to 10 mg of Prednisone

Glucocorticoid Treatment	Dose (mg) Equivalent to 10 mg of Prednisone	Comment
Cortisone	50	Includes parenteral
Hydrocortisone	40	Cortisol
Prednisolone	10	-
Methylprednisolone	8	Medrol: includes parenteral SOLU-MEDROL®
Triamcinolone	8	-
Betamethasone	0.4	-
Dexamethasone	0.4	Oral or parenteral DECADRON®

The designation of a CE-COPD as moderate or severe is denoted by the response to the CRF question “Severity” on the Clinical Exacerbation of COPD CRF page regardless of whether the following CRF questions are answered in the negative or missing:

- “The treating physician elects to administer prednisone (or equivalent glucocorticoid treatment) at least 10 mg prednisone equivalent above baseline, for at least 3 days”
- An unscheduled provider visit such as an office visit, telephone call, urgent care visit, emergency care visit, or hospitalization

A patient may experience more than 1 CE-COPD during the study period.

Clinical Exacerbation of COPD Status: Clinical exacerbation of COPD status is an indicator of whether or not a patient experienced a CE-COPD during study follow-up (Yes, No).

Clinical Exacerbation of COPD Rate: The percentage of patients who experience at least 1 moderate or severe CE-COPD at the end of study follow-up.

Recurrent Clinical Exacerbation of COPD Rate: The percentage of patients who experience more than 1 moderate or severe CE-COPD at the end of study follow-up.

Time to Clinical Exacerbation of COPD: Time, in days, from Study Day 1 to the Date of Symptom Peak plus 1.

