4.4. Replacement of Patients

A patient who is enrolled but does not complete the 12-week intervention period will not be replaced.

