2.3. Sample Size and Power Considerations

Assuming an expected dropout rate of 10%, it is recommended that 400 patients be enrolled so that 360 evaluable patients complete the study. These conclusions are based on a review of the relevant literature, as follows.

Based on previous studies of an exacerbation-prone COPD cohort ([Dransfield et al 2013](#), [Vogelmeier et al 2011](#), [Wedzicha et al 2013](#), [Wedzicha et al 2016](#)), it is expected that 91 (range, 73 to 110) CE-COPD events will occur over the 12-week evaluation period in this study based on reported CE-COPD exacerbation rates of 1.05 and 1.14 events per year. Furthermore, it is expected that 14% (14) of total exacerbations will be severe.

This sample size (ie, n=400 patients, 73 to 110 CE-COPD events) is considered adequate for the fulfillment of the study objectives to evaluate the relationship of albuterol use, inspiratory flow, SDI, and TDS data associated with a subsequent CE-COPD event. Per a previous study ([Jenkins et al 2013](#)), a statistically significant relationship was established between daily SABA usage and subsequent CE-COPD.

In the present study, approximately 73 to 110 CE-COPD events are desired because the model's fitting of the current study involves the analysis of multiple predictors as described in more detail below. Because the largest model considered has 7 covariates, it is desirable to have at least 70 events. The probability to observe at least 70 CE-COPD events is higher than 0.99.

Risk models published in the literature have typically included between 4 and 6 covariates/risk factors ([Bateman et al 2015](#), [Greenberg et al 2012](#), [Quezada et al 2016](#)) to examine the relationship between possible risk factors and a disease. When there is more than 1 covariate (risk factor) in the model, multiple logistic regression may be used to estimate the relationship of a specific covariate of interest (ie, albuterol use) to a primary outcome (ie, CE-COPD), adjusting for the other/remaining covariates (risk factors). In this case, the required sample size to estimate such a relationship is greater than that for univariate logistic regression.

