4. GENERAL ISSUES FOR DATA ANALYSIS

4.1. General

Descriptive statistics for continuous variables include n (number), mean, standard deviation (SD), median, minimum, and maximum. Minimum and maximum will have the same number of decimal points as the original data. Mean and median will have 1 more decimal point than the original data. Reporting of SD will have 2 more decimal points than the original data.

Descriptive statistics for categorical variables include patient counts and/or counts and percentages. Categories for missing data will be presented, if necessary. Confidence intervals (CIs) of means and/or proportions will be reported as specified. Summaries will be provided overall and by CE-COPD status (CE-COPD: No, CE-COPD: Yes, All) and by COPD severity (Yes: Moderate, Yes: Severe) where appropriate.

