7. ENDPOINT ANALYSES

All endpoint analyses will be performed using the ITT analysis set.

Data listings will be presented by patient.

7.1. eMDPI: Albuterol Use

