7.5.2.4. Summary Descriptive Statistics of Initial and Recurrent Clinical COPD Exacerbation Rates

Proportion of patients with at least 1 CE-COPD and proportion of patients with recurrent events will be presented.

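### Event-free withdrawals count as non-events in the crude CE-COPD percentage, putting it about 1 point below the 12-week risk; separately, the Day 84 ±14 window leaves it unstandardized in either direction

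*SAP*

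**What the plan says.** - **Status and rate.** SAP 7.5.1 makes CE-COPD status "an indicator of whether or not a patient experienced a CE-COPD during study follow-up (Yes, No", with no category for an unknown or censored outcome. The rate is "The percentage of patients who experience at least 1 moderate or severe CE-COPD at the end of study follow-up".
- **Reporting.** SAP 7.5.2.4 is one line: "Proportion of patients with at least 1 CE-COPD and proportion of patients with recurrent events will be presented". It mentions no person-time and no censoring.
- **Denominator.** SAP 7 states: "All endpoint analyses will be performed using the ITT analysis set". That set is everyone enrolled.
- **Withdrawal.** SAP 2.3 reads "Assuming an expected dropout rate of 10%, it is recommended that 400 patients be enrolled", and Protocol 4.4 adds: "A patient who is enrolled but does not complete the 12-week intervention period will not be replaced". SAP 4.6 uses the data collected before withdrawal and gives no rule for outcome status afterwards.
- **End of follow-up.** Protocol Table 1 and Appendix B place visit 5 at Day 84 ±14, that is, Day 70 to Day 98.
- **Time to event.** SAP 7.5.1 defines a time from Study Day 1 to symptom peak, but no analysis from Day 1 uses it. The only Kaplan-Meier analysis (SAP 7.5.2.2) covers the 7 days after a landmark use day, and it does censor patients whose follow-up ends early.
- **Sensitivity.** SAP 8 plans none.

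**The concern.** Someone lost on Day 10 without an event enters the percentage exactly as someone seen event-free at Day 84. In a study described as 12 weeks long, readers will take the result as the 12-week risk. It is not that risk, for two separate reasons: withdrawals contribute less than 12 weeks of observation but a full unit to the denominator, and completers stop at different days.

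The same Yes/No split defines the columns of many descriptive tables (albuterol use, inhalational flow, exposure and, within the accelerometry sets, steps and sleep). The 'No' column therefore mixes patients known to be event-free with patients whose 12-week outcome is unknown. The SAP already has a suitable time variable and already censors in one analysis, so leaving censoring out here looks like an oversight more than a decision.

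**Working it through.** **Inputs.** Rates of 1.05 and 1.14 per year (mean 1.095), 10% dropout, 400 enrolled and 360 completing: SAP 2.3. Final visit Day 70 to 98: Protocol Table 1. Assumed, because the documents are silent: a constant event rate, and withdrawal unrelated to risk and uniform over Days 0 to 84.

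**1. The plan's own figure.** 360 × 1.095 × 12/52 = 90.97, i.e. 91 events. The Poisson(91) 2.5% and 97.5% points are 73 and 110, and P(at least 70) = 0.990. The plan's figures reproduce.

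**2. 12-week risk.** Risk to day d = 1 − exp(−1.095 × d/365.25). At d = 84 this is 22.3% (21.5% at 1.05 per year, 23.1% at 1.14).

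**3. Effect of withdrawal alone (completers end at Day 84).** With k = 1.095 × 84/365.25 = 0.2518, the mean observed risk among uniform withdrawals is 1 − (1 − e^−k)/k = 11.6%.
- Crude percentage: 0.9 × 22.3% + 0.1 × 11.6% = 21.2%, which is 1.1 points low.
- Bound, all dropouts leaving on Day 0: 0.9 × 22.3% = 20.0%, which is 2.2 points low.
- Allowing patients to differ in underlying rate (gamma frailty variance up to 1.0), over both planned rates, the uniform-withdrawal shortfall is 0.9 to 1.1 points.

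**4. Effect of the window.**

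| Completers end at | No dropout | Difference from 22.3% | 10% dropout | Difference from 22.3% |
|---|---|---|---|---|
| Day 70 | 18.9% | −3.3 | 18.2% | −4.1 |
| Evenly over Days 70–98 | 22.2% | −0.02 | 21.2% | −1.1 |
| Day 98 | 25.5% | +3.2 | 24.1% | +1.8 |

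Differences are in points, from unrounded values. With 10% dropout, the net error is zero when 0.9 × risk(d) + 0.1 × 11.6% = 22.3%. That gives risk(d) = 23.4% and d of about 89. If completers finish later than that on average, the percentage overstates the 12-week risk.

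**5. Composition of the 'No' group (400 enrolled, completers to Day 84).**
- 'No' patients: 400 × (1 − 0.212) = 315.
- Event-free withdrawals among them: 40 × (1 − 0.116) = 35, or 11%.
- Of those, expected to have an event by Day 84: 40 × (0.223 − 0.116) = about 4, a little over 1% of the 'No' group.

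**6. Which analyses use the 'No' group.** The t-test in SAP 7.1.2.3 and the paired and McNemar comparisons in SAP 7.5.2.1 use only patients with an event. The landmark curves in SAP 7.5.2.2 already censor. The 'No' column appears in descriptive summaries.

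**The case against.** The best defence is that the SAP never calls this percentage a 12-week risk. It says end of follow-up, estimating incidence is not a study objective, and the result is one descriptive line in an exploratory study. The shift of 1.1 points is also small beside sampling error: the 95% half-width at 21.2% of 400 is 1.96 × √(0.212 × 0.788/400), about 4 points. SAP 5.10 and 10.3 report follow-up time by CE-COPD status, and several tables are already scaled to time or shown week by week. All of this stands and limits the weight of the point. It does not remove it: showing unequal follow-up does not correct for it.

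A reader might infer more than the documents support:
- **That the visit window helps to understate the risk.** It is symmetric, and patients followed beyond Day 84 add events.
- **That 11% of the 'No' group is misclassified.** That is the share with incomplete follow-up; about 4 patients would be expected to have a later event by Day 84.
- **That no exacerbation data exist after withdrawal.** Protocol 4.3 asks investigators to attempt to obtain information and to perform the visit 5 assessments if possible. What is missing is scheduled follow-up after that visit.
- **That dropouts have a 135% higher event rate.** The figure in Protocol 3.3 describes heavy reliever users in another study, not dropouts. Risk-related withdrawal is conceivable, since Protocol 4.3 lists interfering illness and prohibited medication as reasons to withdraw a patient, but the documents give no figure for it.

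**Conclusion.** The point holds as a modest one. Counting event-free withdrawals as 'No' puts the crude percentage about 1.1 points below the 12-week risk, and at most 2.2, at the planned 10% dropout with withdrawal unrelated to risk and completers ending at Day 84. The Day 70 to 98 window is a separate defect of standardization whose direction depends on when final visits actually occur. The formal tests are untouched.

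If withdrawal depends on risk, the error could be larger or smaller, and a censored analysis would correct only part of it. Purely as an illustration, give dropouts 2.35 times the rate of completers: the true 12-week risk becomes 24.5%. The crude figure would be 22.5% with uniform dropout, or 21.0% with all dropout in the first 4 weeks; Kaplan-Meier would give 23.5% or 22.7%.

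**What to change.** In SAP 7.5.2.4, keep the planned proportions and add:

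1. The Kaplan-Meier cumulative incidence of first CE-COPD at Day 84 with 95% CI, using the time variable already defined in SAP 7.5.1. Censor at withdrawal, last contact or Day 84, whichever comes first, and treat death without CE-COPD as a competing event. This removes the bias from independent withdrawal and fixes the time point, so it deals with the window as well.
2. Recurrent events per patient-year.
3. A sentence stating that the estimate assumes withdrawal is unrelated to exacerbation risk.

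Keep the 'No' column as planned. Event-free withdrawals may at most be shown as a descriptive sub-column. Replacing the comparator with patients event-free to visit 5 would condition on future completion, while 'Yes' would still include patients who left after an event. That could select a healthier comparator and exaggerate the contrast.

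The cost is a few lines of SAP text, a little extra analysis and one more reported estimate. The dates needed are already collected.
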